## **1.0 Background**

Individuals diagnosed with Parkinson's disease (PD) often suffer from difficulties with gait initiation, maintaining a consistent kinematic gait pattern, and transitions between gait environments. Focused gait training that provides an environment that can emphasize motor control improvement in these deficits would be ideal for building a rehabilitative foundation for gait recovery for individuals with PD.

One approach that has been used to maintain and restore function in other neurological populations with severe disability is gait rehabilitation using treadmill training. This approach allows for specific and repetitive practice of walking movement and can involve therapist or electromechanical assistance. There is preliminary evidence from two small, uncontrolled studies supporting the benefits of therapist-assisted treadmill training on walking, balance, fatigue, spasticity, muscle strength, and quality of life in patients with PPMS and SPMS. Nevertheless, therapist-assisted gait training can require up to three trainers per patient making it burdensome and inefficient in the clinical setting. The intensity of manual treadmill training is low (i.e., <1.5 METs) based in part on the physical capacity and fitness level of the trainers, yet physiological adaptations for optimizing outcomes require moderate or vigorous intensity exercise.

Robotic-assisted gait training (RAGT) addresses many of the limitations of therapist-assisted gait training and can be performed using either exoskeleton or end-effector devices. Exoskeleton devices involve programmable drives or passive elements which physically move the lower limbs, whereas, end-effector approaches involve driven footplates that have trajectories that simulate the stance and swing phases. The G-EO System (Reha Technology AG: Olten, Switzerland) is a novel end-effector robotic gait training system that was developed for regaining mobility and independence in stroke survivors. This system involves minimal therapist and patient burden (e.g., quick set-up, single operate usage), there is the unique capacity for practicing walking and stair climbing movements, and the patient can receive real-time visual feedback. Gait training using the G-EO System has been applied in patients with stroke, Multiple Sclerosis (MS), and cerebral palsy (CP). These studies have established safety and feasibility, and preliminary evidence for benefits on mobility and function. For example, two studies involving 4 weeks of G-EO training with conventional physical therapy in non-ambulatory subacute stroke patients reported improved gait, stair climbing ability, leg strength, and activities of daily living (ADL) compared to physical therapy alone. There is limited RAGT studies evaluating the impact of this type of training for individuals with PD. The potential focus on improved gait kinematics may be of particular benefit for PD patients who often struggle with maintain step length and initiation.

## **2.0 Rationale and Specific Aims**

The logistic advantages and advanced training capabilities of the G-EO System, as well as the benefits reported in other populations, support this strategy as an effective rehabilitation tool for restoring and maintaining function in Parkinson's disease. This approach represents an opportunity for improving current clinical practices for patients with Parkinson's disease. If successful, this project will provide initial evidence for increasing patient access to the G-EO System, and this could be accomplished through "regional technology centers" using a rural health-delivery approach.

The purpose of this study is to investigate the implementation of a novel gait rehabilitation stimulus (G-EO System) that could advance current clinical practices. The goal is to establish the

safety and feasibility of gait training using the G-EO System as well as investigating the impact on mobility, function, quality of life, and participatory outcomes.

**Research Design:** We propose a single-blinded, randomized trial of electromechanically-assisted gait training using the G-EO System in patients with Parkinson's disease with gait disability.

*Specific Aim 1* will establish the safety and feasibility of gait training using the G-EO System.

*Specific Aim 2* will determine the efficacy of gait training using the G-EO System for improving mobility, function, quality of life, and participatory outcomes.

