### **Feasibility and Safety**

Feasibility outcomes will involve process, resources, management, and scientific assessment. Process metrics will include recruitment, retention, and adherence rates assessed by the movement of participants through each stage of the study and training data. Resource metrics will include evaluation of the equipment and facilities through feedback from the therapists. Time to completion relative to proposed target dates will also be reviewed. Management metrics will include data management, documentation of patient progress, record of adverse events, and compliance with approved protocols. Safety will be evaluated through assessment of recorded adverse events.

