## **8.0 Statistical Considerations**

Data will be analyzed using IBM SPSS Version 25.0 (IMB Corps., Armonk, NY). Descriptive statistics will characterize the sample on demographic, clinical, safety, and feasibility metrics. We will compare safety and feasibility between groups using chi-square and *t*-tests for independent samples (*Specific Aim 1*). The efficacy of the intervention on study variables (*Specific Aim 2*) will be examined using a 2 (Group) by 2 (Time), mixed factor ANOVA. A completers analysis will be conducted (i.e.,  $\geq 75\%$  of sessions completed). Effect sizes associated with F-statistics will be expressed as eta-squared ( $\eta^2$ ), and effect sizes based on mean differences will be expressed as Cohen's *d*.

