## **10.0 Follow-up and Record Retention**

Completion of this study is scheduled within approximately 1 year of the first subject enrollment. All patient data will remain coded and stored in locked cabinets up to 6 years following the completion of the study (7 years total). All documents related to this study will be properly shredded when appropriate. All electronic data will be stored as de-identified information in REDCap and on the Microsoft IU Secure Storage System.

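### Aim 1 is to establish feasibility, but no metric has a pass mark, and its only inferential analysis, G-EO versus CPT, cannot show that G-EO training is infeasible when both arms do poorly

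*Combined protocol and SAP*

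**What the plan says.** Section 2.0 (Specific Aims) states that Aim 1 "will establish the safety and feasibility of gait training using the G-EO System".

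Section 5.0 (Feasibility and Safety) lists what will be looked at: "Feasibility outcomes will involve process, resources, management, and scientific assessment". Under process it adds: "Process metrics will include recruitment, retention, and adherence rates assessed by the movement of participants through each stage of the study and training data". On timing: "Time to completion relative to proposed target dates will also be reviewed". No target rate, tolerance or decision rule is attached to any of these.

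Section 8.0 plans two things for these metrics. The first is descriptive: "Descriptive statistics will characterize the sample on demographic, clinical, safety, and feasibility metrics". The second is inferential and is the one labelled Specific Aim 1: "We will compare safety and feasibility between groups using chi-square and" independent-samples *t*-tests.

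Section 10.0 gives a planning horizon: "Completion of this study is scheduled within approximately 1 year of the first subject enrollment".

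**The concern.** Whether G-EO training is feasible in Parkinson's disease is an absolute question about the people allocated to it: do they stay, and do they complete the sessions? A test of G-EO against CPT asks whether the arms differ. The two answers can part company. Both arms can do badly and show no difference, or both can do well and show no difference, and the test returns the same result. Recruitment has no arm at all, because consent and enrolment come before allocation (Section 4.0).

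The descriptive rates do address the absolute question, but the plan does not say what rate would count as feasible or not feasible. That judgement is left until the rates are known. Section 2.0 hopes that a successful project will give initial evidence for wider access to the device, so the feasibility conclusion is meant to be used. Its weight depends on the standard having been set beforehand.

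**Working it through.** **1. Is there a pass mark elsewhere in the plan?** Each number that might serve as one has another job.

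| Figure | Where | What it does |
|---|---|---|
| At least 75% of sessions (0.75 × 12 = 9) | Section 8.0 | Defines the completers analysis |
| Three consecutive missed sessions | Section 5.0, Schedule | Removes a participant from the study |
| 12 visits | Section 5.0, Schedule | Planned treatment course |
| 30 participants | Section 4.0 | Convenience sample |
| About 1 year | Section 10.0 | Planned duration |

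The target dates in Section 5.0 are a benchmark for timing only, with no tolerance and no stated consequence. The plan gives no feasibility target, so there is no figure of its own to reproduce.

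**2. Can the between-group test detect shared failure?** Assumptions: 15 per arm (no allocation ratio is stated), two-sided 0.05, uncorrected Pearson chi-square.

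- If both arms retain 8 of 15 (53%), the two rows of the table are identical, so chi-square = 0 and p = 1.00. The same holds for 6 of 15 (40%) in both.
- Let true retention be 0.60 in both arms. Sum Bin(a; 15, 0.60) × Bin(b; 15, 0.60) over all pairs (a, b) with p ≥ 0.05. The result is 0.951, so about 95% of such trials show no difference.
- Even a real gap is often missed. With 90% against 60%, the power is 0.51 by chi-square and 0.33 by Fisher's exact test.

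**3. How much does a mark chosen afterwards matter?** P(pass) = P(X ≥ c), with X ~ Bin(15, 0.60):

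| Mark c | 9/15 | 10/15 | 11/15 | 12/15 | 13/15 |
|---|---|---|---|---|---|
| P(pass), true 60% | 0.61 | 0.40 | 0.22 | 0.09 | 0.03 |

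**4. What would a mark fixed in advance achieve?** Take 80%, which is 12 of 15. P(X ≥ 12), with X ~ Bin(15, p):

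| True retention p | 60% | 70% | 80% | 90% |
|---|---|---|---|---|
| P(pass) | 0.09 | 0.30 | 0.65 | 0.94 |

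The rule separates 60% from 90% well. It passes a true 70% in 30% of trials and fails a true 80% in 1 − 0.65 = 35%. The exact (Clopper-Pearson) 95% intervals show the same coarseness: 12/15 = 80% (52% to 96%), and 9/15 = 60% (32% to 84%).

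**5. Would an adherence mark add a second check?** Not much. Section 5.0 (Schedule) reschedules cancelled sessions so that 12 are completed before final testing, and drops anyone who misses three in a row. Those who reach the post-intervention assessment will nearly all have passed 9 of 12 sessions, so adherence among the retained is pushed towards 100%. Any adherence rate therefore needs all those randomised to G-EO as its denominator, and a mark on it would largely repeat the retention mark.

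**6. What do the plan's own figures imply for recruitment?** Taking 52 weeks, 6 weeks of treatment and 1 month (4.33 weeks) of follow-up: 52 − 6 − 4.33 = 41.7 weeks, or 9.6 months, and 30 / 9.6 = 3.1 participants per month. This is only a guide. The year is approximate, and Section 5.0 puts the number of treatments ahead of the number of weeks. If the last participant took 10 weeks (an assumption), the enrolment window would be 52 − 10 − 4.33 = 37.7 weeks, or 8.7 months.

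**The case against.** The strongest reply is that this is a small study with a convenience sample, that Section 2.0 speaks of investigating implementation and of initial evidence, and that Section 8.0 will report absolute rates. A reader would see 60% retention and could judge it. On this view *establish* is loose wording and estimation is enough.

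Much of that stands. A reader might infer that the between-group comparison is the only analysis planned for feasibility, that Aim 1 cannot fail, or that its result will carry no information. The documents do not support this. Descriptive statistics on feasibility are planned and will inform, and timing has an informal benchmark. That any rate could be reported as success is an inference from the missing rule, not something the plan says. The reference to success in Section 2.0 concerns the whole project, including efficacy, and not Aim 1 alone.

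It is also fair to say that 15 participants make a blunt instrument (step 4), and that a dated recruitment cut-off would be falsely precise and would measure the site more than the device.

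The reply leaves two things unanswered. Describing a rate does not establish feasibility unless there is something to judge it against, and the one test assigned to Aim 1 addresses a different question.

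**Conclusion.** The concern holds in this form. Aim 1 promises to establish feasibility, no feasibility metric has a pass mark, and the only inferential analysis assigned to Aim 1 cannot show that G-EO training is infeasible when both arms do poorly and cannot apply to recruitment. At a true 60% retention in both arms, the comparison shows no difference in 95% of trials. Choosing the mark afterwards moves the chance of passing a true 60% from 61% to 3%.

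These sizes assume 15 per arm, a 0.05 level, and illustrative true rates, none of which the documents state. The absence of a mark and the mismatch between question and test do not depend on those assumptions. This should be corrected, but it does not invalidate the descriptive results.

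**What to change.** In Sections 5.0 (Feasibility and Safety) and 8.0:

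- Base the feasibility conclusion on absolute rates in the G-EO arm, among all those randomised to G-EO, reported with exact 95% confidence intervals and judged against a mark fixed before data are seen. An example is that at least 80% have the post-intervention assessment. State it as a percentage, since no allocation ratio is given. The 80% is a placeholder that the sponsor may replace.
- Report recruitment pooled over both arms, against the plan's own target of 30 participants with completion in about 1 year, as a separate result on trial conduct and not as a verdict on G-EO training.
- Keep between-group feasibility comparisons as descriptive, and remove recruitment from them.
- State that the rule is coarse with about 15 in the arm, giving the pass probabilities in step 4.

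If the sponsor prefers not to set a mark, Aim 1 should say *estimate* in place of *establish*, with the same intervals reported.

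The cost is a few sentences, with no new data, visits or patients. The downside is that the trial can miss its own mark: with 12 of 15 required, a programme with true retention of 90% would miss it in about 6% of trials, and one at exactly 80% in about 35%.

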### **Assessments**

The study outcomes will be collected by treatment-blinded researchers. All participants on Day 1 who consent to be in the study will complete the following mobility outcomes:

1. Spatial and temporal gait kinematics will be assessed using a PKMAS Zeno Walkway (Protokinetics). Participants will be asked to walk over a 14-foot pressure mat that will capture their gait kinematics and speed. Comfortable and fast walking speed will be assessed. (10 minutes)
2. A 6-minute walk (6MWT) tests to determine walking endurance. Subjects will be asked to walk for 6 minutes along a 30m track. Subjects may stop and rest as often as needed. Subject walking speed will be collected during the test to evaluate rate of functional fatigue. (10 minutes)
3. Balance assessment using the Mini BESTest. Subjects will be asked to complete 14 different tasks ranging from static standing to dynamic walking. All subjects will be guarded closely for safety to prevent falling. (15 minutes)
4. The level of lower extremity functional strength combined with balance will be assessed by the five times sit to stand test. (5 minutes)
5. Performance translation of balance improvement will be measured using the self-report Activities Balance Confidence Scale. (10 minutes)
6. Their level of health-related quality of life assessed by the Parkinson's disease Questionnaire-39. (15 minutes)
7. Obstacle management while walking. Patients will be asked to walk over a flat firm surface for 14 meters. The pathway will include a box that is one foot by one foot that each person. (6 passes; 10 minute break; 6 passes; 10 minute break; 6 passes; 10 minute break) total of 40 minutes
8. Performance translation to real life activities will be measured by accelerometers. Each participant will wear an accelerometer at home to measure activity levels. (completed at home)
- After completing all of therapy, the research team will complete a short interview with the participant. The interview will focus on their experiences during therapy regardless of which group they participated in. We will also ask them to consider how valuable they think the experience was for their health. This interview will take about 15 minutes.

Participants will complete outcome assessments prior to the start of the study, at the end, and one month following completion.

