
## Intervention

The intervention will be delivered through the Neurorehabilitation and Robotics Clinic at the IU Health Neuroscience Center. All rehabilitation training will be supplied by licensed Physical Therapists with oversight from Research Team. The clinicians involved in the delivery of the intervention will not be involved in outcome assessments. All outcome assessment will be completed by the research team. Participants in both conditions will receive conventional physical therapy (CPT) as usual care. Participants in the Robotic training condition will also receive robot-assisted gait training. The standard group will receive traditional overground walking training. This design will control for attention and social contact, total rehabilitation time, and intensity. Both conditions will be delivered at the same frequency (2x/week), duration (40 to 60 minutes), and time frame over 6-weeks. Progression will occur by increasing the session intensity weekly. Training intensity will be monitored and standardized using the Borg Rating of Perceived Exertion scale and will progress from 'fairly light' (11) to 'somewhat hard' (13). This prescription is consistent and appropriate for individuals with Parkinson's patients with mobility

impairment and low fitness levels. Total training time includes both conventional physical therapy (CPT) and gait training (i.e., 30min of CPT + 30min gait training). Training sessions will not exceed 60 minutes. We will record all training parameters. CPT sessions will involve: 3-5 minute warm-up, stretching, progressive strength training exercises, and balance training. Additional strategies for home exercises, fall prevention, and appropriate assistive devices (i.e., orthotics) will be provided universally.

**Conventional physical therapy (CPT):** A CPT session will involve a 3-5 minute warm-up, stretching, progressive strength training exercises, and balance training (for approximately 30 minutes). Gait training will involve traditional activities that involve overground walking activities, object avoidance, and changing speeds/directions (for approximately 30 minutes).

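### Aim 2 sets out to determine efficacy, but at least nine endpoints are tested alike with no primary outcome, decisive test, significance level or multiplicity control

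*Combined protocol and SAP*

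**What the plan says.** Section 2.0 states that Specific Aim 2 "will determine the efficacy of gait training using the G-EO System for improving mobility, function, quality of life, and participatory outcomes". It names four domains and ranks none of them. The same section also uses softer language: the goal is to establish safety and feasibility "as well as investigating the impact on mobility, function, quality of life, and participatory outcomes", and "If successful, this project will provide initial evidence for increasing patient access to the G-EO System".

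The Assessments part of section 5.0 has eight numbered outcome items. The first holds several variables: "Spatial and temporal gait kinematics will be assessed using a PKMAS Zeno Walkway" and "Comfortable and fast walking speed will be assessed". The second begins "A 6-minute walk (6MWT) tests to determine walking endurance" and adds speed during the test as a measure of fatigue. The others are the Mini BESTest, five times sit to stand, the balance confidence scale, the PDQ-39, an obstacle task and accelerometry. Outcomes are collected at baseline, at the end of treatment and one month later.

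Section 8.0 says how Aim 2 is analysed: "The efficacy of the intervention on study variables" is examined with a mixed ANOVA having two groups and two time levels. Eta-squared and Cohen's d are to be reported. The section does not name a primary outcome, the F-test that decides efficacy, the follow-up visit that forms the second time level, a significance level, or any adjustment for multiple tests. Section 4.0 sets a convenience sample of 30 with no power basis.

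**The concern.** An aim to determine efficacy needs a rule for which result answers the question. Here there is none. Every endpoint has equal standing, each ANOVA yields three F-tests (group, time and interaction), and the gait kinematics have no stated number. Nothing limits which significant result may be put forward as the evidence, so the choice can be made after the data are seen.

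The choice among F-tests matters as much as the choice among outcomes. Both arms receive active therapy, so a significant time effect can arise with no added benefit from G-EO. Only the group-by-time interaction, or an equivalent baseline-adjusted group difference, addresses the aim.

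What is at stake is how the result will be read. The protocol hopes to support wider access to the device, and a chance finding on one of many outcomes could be presented as evidence of efficacy.

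**Working it through.** The documents give no alpha, power or detectable effect, so there is no figure of theirs to reproduce.

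**Inputs from the documents**
- Endpoints (Assessments): comfortable speed, fast speed, 6MWT, Mini BESTest, sit to stand, balance confidence, PDQ-39, obstacle task and accelerometer, giving k = 9. Gait kinematics and 6MWT fatigue rate would add to this, so nine is a minimum.
- Sample size (section 4.0): 30 in total.

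**Assumptions, not in the documents**
- Two-sided 5% for each test.
- 15 per arm, because no allocation ratio is stated.
- No true effect on any outcome.
- One decisive test per endpoint. In a two-by-two mixed ANOVA the interaction test is equivalent to a two-sample t-test on change scores, so the correlations below are between changes in different outcomes.

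**Independent endpoints**
- At least one false positive in either direction: 1 − 0.95^9 = 1 − 0.630 = 37.0%.
- Eight endpoints instead of nine: 1 − 0.95^8 = 33.7%.
- At least one false positive favouring G-EO: 1 − 0.975^9 = 1 − 0.796 = 20.4%, against 2.5% for a single test.

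**Correlated endpoints**

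Simulated two-sample t-tests, 15 per arm, nine equally correlated outcomes, 40,000 replicates:

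| Pairwise correlation | Any false positive | Favouring G-EO |
|---|---|---|
| 0.3 | 32.8% | 16.6% |
| 0.5 | 27.2% | 13.7% |
| 0.7 | 20.6% | 10.2% |

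The two-sided rate is therefore about four times nominal (20.6/5 = 4.1) to seven times nominal (37.0/5 = 7.4).

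**Sensitivity to the assumed level and the number of tests**
- At 1% per test: 1 − 0.99^9 = 8.6%.
- The two-sided rate passes one half only at 14 independent tests: 1 − 0.95^13 = 48.7% and 1 − 0.95^14 = 51.2%. At 14 tests with correlation 0.5 it is 35.4%.

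**Why one primary outcome rather than adjusting over nine**
- Bonferroni: 0.05/9 = 0.0056 per test.
- With 15 per arm, no dropout and a comparison that ignores baseline, 80% power needs a standardised difference of 1.06 at 0.05 and 1.42 at 0.0056. The ratio is 1.42/1.06 = 1.34.
- For a change-score test both figures are multiplied by √(2(1 − r)), where r is the baseline-to-post correlation. The documents do not give r. At 0.05 the detectable difference is 1.06 at r = 0.5, 1.06 × √0.6 = 0.82 at r = 0.7, and 1.06 × √0.4 = 0.67 at r = 0.8. The 1.34 penalty is the same at every r.

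**The case against.** The best defence is that this is an early study. Its first aim is safety and feasibility, the sample is one of convenience, section 2.0 speaks of initial evidence, and section 8.0 commits to effect sizes as well as tests. Read that way, Aim 2 is exploratory and formal error control is optional. This has weight: it is the reason to recast the aim rather than demand a confirmatory design. It does not remove the gap. The formal aim and section 8.0 both still speak of efficacy, no confidence intervals are planned, and nothing limits which significant result may support the claim.

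A reader might infer stronger conclusions that the documents do not support:
- **That a false-positive efficacy claim is likely.** Over nine endpoints no computed rate reaches one half. These rates assume no true effect anywhere, and a false claim also requires a single positive result to be read as efficacy. The plan states no success rule either way.
- **That 5% per test is the plan's rule.** It is an assumption; the missing level is part of the gap.
- **That the tests should be doubled to 18 for two follow-up visits.** The ANOVA has two time levels, so this does not describe the planned analysis. The unassigned one-month visit is a separate omission.
- **That only very large effects can be detected.** The value of 1.06 is for a comparison ignoring baseline. The interaction test can detect less than that if the baseline correlation is above 0.5.
- **That only the obstacle task is affected by what each arm practises.** The conventional arm's gait training covers "overground walking activities, object avoidance, and changing speeds/directions", while the G-EO arm's gait training is on driven footplates. The same caveat applies to overground walking speed and the 6MWT.

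**Conclusion.** The concern holds as a defect in the analysis plan. Aim 2 promises an efficacy determination that section 8.0 cannot deliver with a known error rate, because no outcome, F-test, significance level or multiplicity rule is fixed for at least nine endpoints.

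At an assumed two-sided 5% per test and under no true effect, the chance of at least one false-positive result is at most 37% for nine endpoints, and about 20 to 33% if they are moderately to strongly correlated. For a false result favouring G-EO it is about 10 to 20%. These figures count nine endpoints and one test each; analysing the unnamed kinematics or reading other F-tests as evidence would raise them by an amount the documents do not fix.

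This should be corrected. It does not call for a change in design or sample size.

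**What to change.** Make these changes before any outcome data are analysed by group. Only outcome assessors are blinded and no unblinding event is defined, so that is the usable deadline.

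1. In section 8.0, name one primary efficacy outcome, one time point (for example the post assessment) and one contrast (the group-by-time interaction or an equivalent baseline-adjusted group difference), tested at two-sided 5%.
2. Label every other outcome, including the gait kinematics, as secondary or exploratory, and report each with a 95% confidence interval.
3. Reword Aim 2 so that it estimates preliminary efficacy with 95% confidence intervals.
4. Leave the choice of primary outcome to the sponsor, with a written justification that addresses the training difference. Overground walking, object avoidance and speed changes are rehearsed in the conventional arm's gait training, so the caveat covers walking speed and the 6MWT as well as the obstacle task.

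The cost is protocol and SAP wording only, with no extra participants, visits or data. The downside is that secondary outcomes can no longer support a stand-alone efficacy claim. A single primary outcome holds the false-positive rate of the efficacy test at 5% without the 1.34-fold increase in detectable effect that Bonferroni over nine endpoints would impose.
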